Consent was obtained in a quiet setting prior to the initiation of the study. The legal guardian was given opportunity to delay consent until he/she has taken adequate time to read and understand the written consent and discuss the study with others. Subjects were not consented in writing

until they were able to demonstrate adequate understanding of all aspects of the study and consent process. A copy of the consent form was given to the patient/legal guardian. The signed consent form remained in the patient's study files at the clinical center.

Randomization:

All enrolled subjects were randomized according to a permuted-block design to receive either placebo (saline) or AZM (Fresenius Kabi, USA) at 10mg/kg/day (referred to as "standard dose") or 20mg/kg/day (referred to as 'high dose') intravenously (IV) every 24 hours for 3 days. The randomization schedule was created by the study biostatistician and provided to the study pharmacist for implementation. The FDA required the study enrollment to be done in two stages, Stage 1: First 9 subjects (older than 6 months), and Stage 2: Remaining 39 subjects (of all ages) if no safety issues were found. The first stage enrolled 9 subjects equally to the 3 treatment groups. For this, the random assignment of treatment was determined by random permutation. For the second stage, we randomly assigned the 3 treatments equally to the 39 subjects using block randomization of size 3 or 6. In addition, to maintain blinding to the treatment assignment, placebo was randomly assigned to either 10 mg/kg or 20 mg/kg dose. [name] generated the randomization schedule as described above. [name] provided the randomization schedule (with randomization IDs) in an excel file to the study pharmacist in charge of dispensing the appropriate treatment.

Duration of Study:

The trial began in February of 2016, and due to the age restriction placed by the FDA, the first 9 subjects enrolled were older than 6 months of age. Once this number was attained, and no safety

concerns were evident as determined by the DSMB, infants younger than 6 months of age were eligible for enrollment in the study. The study spanned three and a half RSV seasons, with the last patient enrolled in February of 2019. The trial ended once 48 subjects were enrolled into the study. All subjects completed the study. No long term follow up was provided.

Primary and Secondary Outcomes

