The primary outcomes of this trial were to ascertain 1. The safety and AZM pharmacokinetic and 2. If treatment with AZM resulted in decreased nasal MMP-9 levels. Notably, when the study protocol was expanded to include non-ventilated patients, the primary outcome also changed from endotracheal MMP-9 to nasal MMP-9 levels. The secondary outcomes were to determine the *in vivo* efficacy of AZM administration on improving clinical outcome measures, specifically duration of ventilatory support and oxygenation, as well as PICU and hospital length of stay. The CONSORT guideline was used for the reporting of this trial.

Visit Schedule and Study Procedures

Overview:

If subjects met the inclusion criteria and have no contraindication to study participation, they were be enrolled into the study within 48 hours of positive pressure ventilation. Subjects were randomized via a permuted block design to receive either placebo (normal saline), 10mg/kg of IV azithromycin or 20 mg/kg of IV azithromycin, daily for 3 days. Prior to drug administration, assessment was performed to ensure that subjects do not have contraindications of AZM administration or development of any adverse events. Nasal and endotracheal aspirate (if

intubated) were obtained daily for the first 3 days (first sample obtained before drug administration).

Prior to drug administration, baseline labs (CBC with differential, liver and renal function, electrolytes) was reviewed. If the patient had evidence of hypokalemia, hypocalcemia or hypomagnesemia, the electrolyte abnormalities were corrected prior to drug administration. EKG was also reviewed, and if there was evidence of prolonged QT, the subject was excluded from the study. Vital signs (heart rate, blood pressure, temperature, saturations), ventilator or BiPAP or HFNC settings, presence of multi-organ failure were recorded. All these parameters were assessed prior to drug administration. Vital signs (heart rate, blood pressure, temperature, saturations) were also assessed immediately before the drug infusion, during, and 2 and 4 hours post completion of infusion.

During the hospitalization, all patients were treated according to the American Academy of Pediatrics guidelines for the management of bronchiolitis, namely supportive care. All decisions regarding medical treatment during hospitalization were made by the patient's primary care team.

Data Collection:

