All participant data were obtained and recorded in individual files that was stored in a secured file cabinet within a locked office. Upon study entry, all participants were given a unique identifier to be used through the entirety of the study and this too was maintained in a locked file cabinet in secured office. Following each study visit, the data obtained was entered into a database using the study participants' unique identifiers. All other personal data were omitted from electronic records. At the close of the study, any missing data was verified with chart review. Only authorized study personnel have access to patient data.

Data Analysis

The primary outcome measured was MMP-9 activity. Based on our preliminary data, we expect that n=16 per group would be sufficient to detect a 20% and 25% decrease in MMP-9 activity in the treated group (10mg/kg and 20mg/kg; respectively) relative to placebo with 80% power.

[name] (Professor, UAB School of Public Health) is the biostatistician for this clinical trial.

Nasal and Endotracheal Aspirate Collection and Processing

Nasal samples were collected using a nasal swab inserted through the nares parallel to the palate (not upwards) until resistance was encountered or the distance inserted was equivalent to that from the nostril to the ear of the patient indicating contact with the nasopharynx. After gentle rubbing and rolling of the swab, it was left in place for several seconds to absorb secretions prior to removal. The swab was then immediately placed into a sterile vial containing 3 ml of viral transport media (Quidel, San Diego, CA), and kept at 4°C for further analysis.

Endotracheal aspirates were collected via endotracheal tube suctioning using an 8 Fr suction cannula (CareFusion, San Diego, CA, USA) and centrifuged at 500xg for 10 min to separate supernatant from cells and mucus (pellet) . Separate aliquots of supernatant were subsequently saved at 4°C for further analysis.

Assay of AZM, Urea and Pharmacokinetic Analysis

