This study was designed to have a total sample size of 48 participants divided into three groups, with 16 per group to detect a 25% and 37.5% decrease in lung MMP-9 activity in the treated groups (10mg/kg and 20mg/kg, respectively) relative to placebo with 80% power using analysis of variance. The assumptions were based on MMP-9 levels found in endotracheal aspirate of children with RSV-induced respiratory failure (Kong et al, *ERJ* 2014).

Means, standard deviations, medians, quartiles and range (minimum, maximum) described continuous variables and counts and percentages for categorical variables. To compare baseline characteristics among the treatment groups, we used Kruskal-Wallis test for age, height and weight due to evidence of non-normality of the distribution of the values. We used either Chi-Square or Fisher's exact test for categorical variables depending on expected cell counts.

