We analyzed inflammatory markers by first performing \log_{10} transformation to address the skewness of the distribution and extreme outliers. We then calculated the difference at each time point relative to baseline to obtain the change (i.e. pre and post treatment) outcome and fitted a generalized linear mixed model (GLMM) with random intercepts and assumed unequal variances across treatment groups with change from baseline as the outcome. The model included treatment, day and treatment by day interaction. Point and confidence interval estimates of the mean change outcome at each time point and treatment group combination were obtained. If a confidence interval for the mean change does not include 0, this is evidence of an effect associated with that particular treatment as it is either a significant increase (or decrease) in the inflammatory marker relative to baseline. The Bonferroni approach was used to adjust for multiple testing and simultaneous confidence intervals. Thus, significance was determined using a cut-off of 0.002 and a 99.8% level was used to construct confidence intervals for each for each treatment at each time point. Note that the sample size justification was based on the assumption that the MMP-9 levels are normally distributed with common standard deviation. However, in the data for this trial, we observed evidence of non-normality and non-constant variance across the treatment groups. Thus, GLMM was deemed more appropriate than ANOVA. Furthermore, fitting GLMM allows us to combine unbalanced data from different time points to help gain more power in evaluating treatment effect.

We used a generalized linear model assuming a negative binomial distribution for clinical outcomes (measured in number of days), using log link to address possible overdispersion due to some extreme observations. Furthermore, we fitted a model that allowed the variance to differ by treatment group. Spearman Correlation was used to examine associations. For this set of

analyses, the standard 5% level of significance and 95% confidence interval was used as these are all exploratory outcomes. All analyses were done using SAS version 9.4.

IRB and IND

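### The marker analysis, including primary nasal MMP-9, judges each arm against its own baseline and specifies no azithromycin-minus-placebo comparison, so a change common to all arms can be read as a drug effect

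*Combined protocol and SAP*

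**What the plan says.** Primary and Secondary Outcomes poses the efficacy question as "If treatment with AZM resulted in decreased nasal MMP-9 levels". The Design section describes a masked, placebo-controlled trial with three groups. Both sizing statements take placebo as the reference: Data Analysis has "10mg/kg and 20mg/kg; respectively) relative to placebo with 80% power", and Sample Size Determination and Statistical Analysis has "relative to placebo with 80% power using analysis of variance".

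The marker analysis, in the latter section, fits a mixed model to the log10 change from baseline with terms for treatment, day and their interaction. It reports a mean change with a confidence interval for each arm at each time point. The rule for reading these is "If a confidence interval for the mean change does not include 0, this is evidence of an effect associated with that particular treatment", and the same sentence makes baseline the reference. The adjusted level is attached to the same quantities: "a 99.8% level was used to construct confidence intervals for each for each treatment at each time point".

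Nowhere do the documents name, for any marker, a dose-minus-placebo difference, another between-arm contrast, or a test of the treatment or interaction term. The same section describes data already seen: "However, in the data for this trial, we observed evidence of non-normality and non-constant variance across the treatment groups".

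**The concern.** A change from baseline within one arm mixes whatever the drug does with whatever would have happened without it. Children enter early in a severe acute illness, and "all patients were treated according to the American Academy of Pediatrics guidelines for the management of bronchiolitis, namely supportive care". MMP-9 could therefore rise or fall over the sampling days in all three arms. The placebo arm exists to remove that common movement, and the written rule does not use it.

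Two consequences follow. The error rate of the rule depends on a quantity that the documents do not give. Also, since Randomization counts placebo among the treatments ("we randomly assigned the 3 treatments equally to the 39 subjects"), a literal reading would credit saline with an effect whenever its own interval excludes 0. At stake is the efficacy conclusion on the primary marker.

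**Working it through.** **Inputs from the documents.** Three arms of 16. Three daily samples, the first before dosing, so two post-baseline days. Cut-off 0.002 with 99.8% intervals. Target decreases of 25% and 37.5% (Sample Size Determination and Statistical Analysis) or 20% and 25% (Data Analysis), each with 80% power.

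**Assumed.** The documents give no SD, no correlation between days and no natural-course change in MMP-9. Shifts are in SD units of change. The correlation between days is 0.5 unless stated, and data are complete (the plan's data are unbalanced).

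**1. The plan's own sample size.** It cannot be reproduced, because neither an SD nor an alpha is stated. Assuming an omnibus F test at 0.05, the SD can be solved from noncentrality λ = n·Σ(μᵢ − μ̄)²/σ² on 2 and 45 df.
- Means 1, 0.75, 0.625: Σ = 0.0729 and 16 × 0.0729 = 1.167. Power of 80% needs λ ≈ 10.30, so σ ≈ 0.3365 of the placebo mean.
- Means 1, 0.80, 0.75: Σ = 0.035 and 16 × 0.035 = 0.56, so σ ≈ 0.2331.

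These SDs are used only for the cost of the fix. The concern does not rest on them.

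**2. One arm, one day.** The 99.8% interval excludes 0 when |mean|/(s/√16) exceeds t(0.999, 15 df) = 3.733. If every arm shifts by d SD and the drug does nothing, the statistic is noncentral t with noncentrality 4d. The probabilities are 0.2%, 1.3%, 8.2%, 29.0% and 60.9% for d = 0, 0.25, 0.5, 0.75 and 1.0. They are the same for placebo as for either dose.

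**3. The rule over two doses and two days.** Simulation, 100,000 trials per shift, no drug effect. The first two result columns give the chance that at least one active-arm interval excludes 0.

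| Shared shift (SD) | One-sample t | Random intercept, arm-specific variances | Any of 4 dose-minus-placebo contrasts, alpha 0.002 |
|---|---|---|---|
| 0 | 0.8% | 0.8% | 0.7% |
| 0.25 | 4.6% | 5.2% | 0.7% |
| 0.5 | 27% | 30% | 0.7% |
| 0.75 | 69% | 73% | 0.7% |
| 1.0 | 95% | 97% | 0.7% |

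At alpha 0.0125 the four contrasts give about 4.4% at every shift. Varying the correlation from 0.8 to 0.2 moves the random-intercept column to 4.3%–5.6% at 0.25 SD, 24%–33% at 0.5, 64%–80% at 0.75 and 93%–98% at 1.0.

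**4. Comparing arms by eye.** Suppose the rule is softened to: an active arm is significant and placebo is not. With one-sample t intervals, correlation 0.5 and no drug effect, that pattern still occurs in about 23% of trials at 0.5 SD, 38% at 0.75 SD and 21% at 1.0 SD (40,000 trials each).

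**5. The adjustment.** 0.05/0.002 = 25 comparisons, but the family is not listed. Bonferroni limits false positives when the true change is zero. It does nothing when all arms move together.

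**The case against.** The strongest reply is that the model already contains treatment and treatment-by-day terms, that the section speaks of evaluating a treatment effect, and that the tests behind the 0.002 cut-off are not named. Between-arm tests may therefore have been run. This is fair as far as it goes: the text fixes one rule of interpretation and does not show that nothing else was computed. But a model that could supply a contrast is not a plan that specifies one, and the only conclusion the text ties to a result is the within-arm one.

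A second reply is that the size is hypothetical. That stands. With no shared shift the rule errs 0.8% of the time, and the documents do not say how far MMP-9 moves. The larger percentages show how the rule behaves; they do not estimate what happened in this trial.

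Third, care was guideline-based but left to each primary team, so it was not identical across patients. True, but the argument needs only that a common change is possible.

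Fourth, this is a pilot. The section applies its exploratory label to the day-count clinical outcomes and the correlations. It holds the markers to an adjusted significance level.

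**Conclusion.** The concern holds and must be fixed. As written, the conclusion on the primary marker does not use the randomised comparison, and a change shared by all arms can be declared an azithromycin effect. The excess error is negligible with no shared shift. It reaches about 5% at 0.25 SD of change, 27% to 30% at 0.5 SD and 95% to 97% at 1 SD, assuming 16 complete patients per arm and days correlated 0.5. Dose-minus-placebo contrasts do not depend on the shift. That the rule lacks a placebo reference follows from the text alone; only the size rests on these assumptions.

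**What to change.** Base the nasal MMP-9 conclusion on the difference in mean log10 change between each azithromycin dose and placebo, from the same mixed model, at both post-baseline days (Days 2 and 3), with confidence intervals. Name the MMP-9 measure, since active and total MMP-9 are both assayed.

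Match the level to the count. For one measure, 2 doses × 2 days = 4 contrasts, so 0.05/4 = 0.0125 and 98.75% intervals. For both measures there are 8, so 0.05/8 = 0.00625. If 0.002 is kept, list the tests it covers. State that the contrasts, and any level looser than 0.002, were set after the data were seen, and do not choose a single day now. Use the same form of contrast for any other marker on which a treatment claim is made. Keep within-arm intervals as description, and reword conclusions that rest on them.

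**Cost.** Four ESTIMATE statements per measure and some rewording; no new data. Half-widths in SD of change, from simple t intervals:
- current within-arm 99.8%: 3.733/√16 = 0.93
- contrast at 98.75%: 2.657 × √(2/16) = 0.94
- contrast at 99.8%: 3.385 × √(2/16) = 1.20

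Precision is thus almost unchanged at 98.75% and about 1.20/0.93 = 1.3 times wider at 99.8%.

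Pairwise power under the back-solved SDs (two-sample t, 30 df), lower dose then higher:

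| Alpha | 25% and 37.5% decreases, SD 34% | 20% and 25% decreases, SD 23% |
|---|---|---|
| 0.05 | 53%, 86% | 65%, 84% |
| 0.0125 | 31%, 69% | 42%, 65% |
| 0.002 | 12%, 43% | 20%, 38% |

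These powers are only a guide: they are on the raw scale rather than log10 change, and the 25% and 37.5% target was set for lung rather than nasal MMP-9. Some within-arm effects may no longer count as evidence of a drug effect.

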Nasal, endotracheal aspirates (if intubated) and serum samples were obtained once daily for the first 3 days. The collection window had at least 24 hours between each sample collection. If patients were extubated within the first 3 days of study window, only nasal samples will be collected. Clinical data was collected each day until the subject was discharged from the ICU.

An overview of clinical and biologic data is outlined in this table.

	Day 1	Day 2	Day 3	Day of PICU discharge	Day of hospital discharge
AZM level (serum, nasal, lung)	X	X	X		
RSV titer (nasal and lung)	X	X	X		
Active MMP-9, Total MMP-9, TIMP (nasal and lung)	X	X	X		
Other RSV cytokine activity (nasal and lung)	X	X	X		
Continous vital signs monitoring ¹	X	X	X		
Baseline and continous lab review ²	X	X	X		
Electrocardiogram	X	X	X		
Study drug administration ³	X	X	X		
Duration of positive pressure ventilation (MV, BiPAP, HFNC)	X	X	X	X	X
Duration of oxygenation	X	X	X	X	X
Duration of PICU stay				X	
Duration of hospital stay					X

¹All assessments were done prior to dosing, during dosing until completion of infusion, immediately at the end of infusion, 2 and 4 hours post completion of infusion.

²Laboratories that were collected: CBC with differential, electrolytes, liver and renal function; record if done for clinical care.

³Study drug administration took place on 3 consecutive days (1 dose per day) after consenting. Study drug at 2 mg/ml was administered over 60 minutes.

Withdrawal of Participant Consent and Discontinuation of Study Drug:

Study participation may be discontinued for any of the following reasons:

- a. Subject decision to withdraw consent for study
- b. Evidence of allergy to administered products
- c. Intolerable adverse event as judged by study investigator

Safety Data

Adverse Events:

- a. Adverse event: Any untoward medical occurrence in a patient or clinical investigation in which a subject is given a pharmaceutical product; does not necessarily have a causal relationship with such treatment, or
- b. Any unfavorable and unintended sign (including abnormal laboratory findings), symptom, or disease temporally associated with the use of a medicinal (investigational) product; not necessarily related to the product.
- c. Change-from-baseline

AEs can take 2 forms:

- i. Appearance of a new symptom or sign, or
- ii. Increased severity or frequency of an existing symptom or sign

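### Does the unexplained Bonferroni cut-off of 0.002 for the inflammatory markers need to be re-derived?

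*Combined protocol and SAP*

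**What the plan says.** The section Sample Size Determination and Statistical Analysis log-transforms the markers and fits a mixed model to change from baseline. The output is then described: "Point and confidence interval estimates of the mean change outcome at each time point and treatment group combination were obtained". An interval that excludes zero is given a meaning: "this is evidence of an effect associated with that particular treatment". Multiplicity is handled in two sentences. The first is "The Bonferroni approach was used to adjust for multiple testing and simultaneous confidence intervals"; the second gives the level: "significance was determined using a cut-off of 0.002 and a 99.8% level was used to construct confidence intervals".

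The same section sets a different rule for the clinical outcomes and correlations: "the standard 5% level of significance and 95% confidence interval was used as these are all exploratory outcomes". Primary and Secondary Outcomes names one biologic question as primary: "If treatment with AZM resulted in decreased nasal MMP-9 levels". The schedule table under Data Collection lists active and total MMP-9, TIMP and other cytokines, each in nasal and lung samples. No section gives the size of the Bonferroni family or the overall level for the marker analyses.

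**The concern.** A Bonferroni cut-off is an overall level divided by a number of tests. Here the quotient is given without either input, although it is presented as following from the method. The only conventional level in the section, 5%, belongs to the analyses called exploratory.

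Two misreadings are possible. If the intervals are taken as simultaneous at 5% over every marker, arm and day, an isolated cytokine finding looks better protected than it is. If MMP-9 shows no effect, part of the reason could be a cut-off sized for many markers and applied to the primary one, with only 16 patients per arm. Because an interval excluding zero is the decision rule, the choice of level decides which marker changes are declared.

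**Working it through.** **Inputs**

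- Cut-off 0.002 and interval level 99.8% (Sample Size Determination and Statistical Analysis).
- 3 treatment groups (Design).
- 2 post-baseline days: three daily samples, the first before dosing (Visit Schedule and Study Procedures).
- 13 markers: active MMP-9, total MMP-9, TIMP-1 and ten cytokines (Biologic Outcome Measurement). RSV load is left out.
- 2 compartments, nasal and lung (table under Data Collection).
- Overall level: not stated; 5% is assumed.

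**Step 1: the plan's own figure.** 1 − 0.002 = 0.998, so the two stated levels agree. The implied count is m = 0.05/0.002 = 25. With rounding to three decimals, 0.05/21 = 0.00238 and 0.05/33 = 0.00152 both print as 0.002, so m from 21 to 33 fits. The count depends on the assumed level: at 10% it would be 0.10/0.002 = 50. The exact derivation cannot be recovered.

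**Step 2: counts from the documents.** The required cut-off is 0.05/m. The bound on the family-wise error at the cut-off used is m × 0.002.

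| Family | m | 0.05/m | m × 0.002 |
|---|---|---|---|
| One nasal MMP-9 measure, 3 arms × 2 days | 6 | 0.0083 | 1.2% |
| Active and total nasal MMP-9, 3 × 2 | 12 | 0.0042 | 2.4% |
| Active and total MMP-9, both compartments, 3 × 2 | 24 | 0.0021 | 4.8% |
| One treatment test per marker and compartment, 13 × 2 | 26 | 0.0019 | 5.2% |
| 13 markers × 2 days within one arm | 26 | 0.0019 | 5.2% |
| 13 markers, one compartment, 3 × 2 | 78 | 0.00064 | 15.6% |
| 13 markers, both compartments, 3 × 2 | 156 | 0.00032 | 31.2% |

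The three families with 24 or 26 members all round to 0.002. The 24-interval family covers every MMP-9 interval. The first 26-member family covers every listed marker and compartment for tests, though not every interval. The second is per arm only; over three arms it becomes the 78 intervals and 15.6%.

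**Step 3: cost to the primary marker.** Interval width is proportional to the critical value. With 15 degrees of freedom (one arm of 16 with its own variance) the values are 3.733 at 0.002 and 3.036 at 0.0083; with the normal distribution they are 3.090 and 2.638. The width ratios are 3.733/3.036 = 1.23 and 3.090/2.638 = 1.17. If both MMP-9 measures count (0.0042), the values are 3.375 and 2.865, and the ratios are 3.733/3.375 = 1.11 and 3.090/2.865 = 1.08.

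**Step 4: what separate families would do.** With one MMP-9 measure taken out, 12 markers × 6 = 72 intervals remain, and 0.05/72 = 0.00069. The critical values are 4.253 (15 df) and 3.392 (normal), so those intervals become 4.253/3.733 = 1.14 or 3.392/3.090 = 1.10 times wider. MMP-9 would get narrower intervals, but at a level chosen after the data were seen.

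**The case for a change.** The strongest case for acting is that the section calls the intervals simultaneous without saying over what. Several families fit 0.002 and they protect different claims. None of those that fit makes every marker interval in every arm simultaneous at 5%. Naming the family, the count and the overall level would take one sentence, and without it a reader cannot say what a single cytokine interval excluding zero is worth. The 80% power statements (Data Analysis; Sample Size Determination and Statistical Analysis) also give no significance level, and the latter rests on analysis of variance rather than on these intervals.

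The omission stands. What does not stand is the step from a missing description to a faulty threshold. The per-interval error is stated, and m × 0.002 bounds the error for any set of intervals fixed in advance; any such set of up to 25 stays within 5%. Nasal MMP-9 falls well inside that limit. The plan ranks no cytokine as a primary or secondary outcome and never claims 5% control over 78 or 156 intervals; in a pilot trial those results would be read as exploratory in any case. On power, the section itself discloses that the sample size assumed normality and a common standard deviation and that the mixed model later replaced analysis of variance. A missing level in the power statement does not affect the validity of the intervals.

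**Conclusion.** This is a gap in description, not an error in the analysis. At an assumed overall 5%, 0.002 agrees with families of 24 or 26. Whichever was intended, the primary nasal MMP-9 comparisons carry a bound of 1.2% (six intervals) or 2.4% (twelve). For the primary outcome the cut-off errs on the strict side, at a price of 8% to 23% in interval width depending on whether one or two MMP-9 measures count and on the degrees of freedom.

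Re-cutting the levels would gain nothing. Enrolment ended in February 2019 and the section already describes features of the observed data, so a looser MMP-9 level could only sit beside the 0.002 result as a post hoc supplement. A stricter level for the other markers would widen their intervals by 10% to 14% to protect a claim the plan does not make. An analyst can read the results sensibly as they stand: take MMP-9 at 0.002 as conservative, and treat isolated findings on the other markers as exploratory.

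The conclusion rests on the assumed 5% overall level, on counts derived from the listed markers rather than printed, and on each interval having its nominal coverage. It concerns only the multiplicity level. Whether change within an arm is the right basis for a treatment claim is a separate question.

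### The 80% power for MMP-9 is stated without an alpha or multiplicity adjustment and is never related to the 0.002 cut-off at which MMP-9 is judged

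*Combined protocol and SAP*

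**What the plan says.** MMP-9 is a primary outcome (Primary and Secondary Outcomes, where it is nasal MMP-9) and is the outcome that sized the trial. Two sections give the power:

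- Data Analysis: "n=16 per group would be sufficient to detect a 20% and 25% decrease in MMP-9 activity", with 80% power.
- Sample Size Determination and Statistical Analysis: "with 16 per group to detect a 25% and 37.5% decrease in lung MMP-9 activity in the treated groups", "relative to placebo with 80% power using analysis of variance".

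Neither section states a significance level, an SD or a multiplicity adjustment.

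The analysis text of the second section covers inflammatory markers as a class. They are log10-transformed, expressed as change from baseline and fitted with a mixed model (GLMM). A marker shows an effect in an arm if the interval for that arm's mean change at a time point excludes zero. "The Bonferroni approach was used to adjust for multiple testing and simultaneous confidence intervals", and hence "significance was determined using a cut-off of 0.002 and a 99.8% level was used to construct confidence intervals". No marker is exempted, and the same paragraph goes on to discuss MMP-9. The number of tests behind 0.002 is not stated; 0.05/0.002 = 25 would fit a 5% family level.

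The section concedes that the sample size assumed that "MMP-9 levels are normally distributed with common standard deviation", says that the data did not bear this out, and presents the GLMM as a way to gain power. It does not mention what the stricter cut-off does to power. The only explicit 5% level is for the clinical outcomes and correlations, which it calls exploratory.

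**The concern.** The 80% is the sole justification for 16 per group. Power depends on the significance level, so a figure without an alpha cannot be carried to a much stricter threshold. As written, a reader would attach it to the MMP-9 result reported at 0.002.

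That matters most if the result is null. Failure to reach 0.002 would be read as negative evidence from an 80%-powered test, and the documents do not support that reading. The account of power is also one-sided: it reports the gain hoped for from the GLMM and leaves out the cost of the cut-off. Meanwhile the outcome that sized the trial faces a threshold 25 times stricter than the exploratory clinical outcomes.

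**Working it through.** **Inputs from the documents.** Three groups of 16 ("total sample size of 48 participants divided into three groups"); ANOVA; 80% power; decreases of 25% and 37.5% (Sample Size section) or 20% and 25% (Data Analysis); cut-off 0.002.

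**Not given, so assumed.** The design alpha, taken as two-sided 5% and then varied. The SD is also missing, but step 2 does not need it.

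**Step 1. The plan's own figure.** Without an alpha and an SD, the 80% can be neither reproduced nor refuted. One can only ask what it implies. For a one-way ANOVA, power = P(F′(2, 45, λ) > F crit), with λ = n Σ(μᵢ − μ̄)²/σ². At 5%, F crit = 3.20, and 80% power needs λ = 10.31.

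The implied SD, as a fraction of the placebo mean, is √(16 Σ(μᵢ − μ̄)²/10.31):

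- Means 1, 0.75, 0.625: Σ = 0.0729, SD = √(1.1667/10.31) = 0.34.
- Means 1, 0.80, 0.75: Σ = 0.0350, SD = √(0.560/10.31) = 0.23.

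**Step 2. The same ANOVA at 0.002.** F crit rises to 7.16. With λ = 10.31, power is 35.4%. This depends only on λ, so it is the same for either pair of effect sizes.

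| Assumed design alpha | λ for 80% power | Power at 0.002 |
|---|---|---|
| 10% | 8.12 | 24% |
| 5% | 10.31 | 35% |
| 2.5% | 12.49 | 47% |
| 1% | 15.41 | 61% |
| 0.5% | 17.65 | 70% |
| 0.2% | 20.68 | 80% |

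A two-group t-test set to 80% at 5% gives a similar answer at 0.002: 34% with 30 df, 35% with 45 df.

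**Step 3. What would restore 80% at 0.002, from a 5% design.**

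- Sample size: λ grows as 10.31 × n/16. At n = 30, λ = 19.32 and power on (2, 87) df is 80.1%; at n = 29 it is 77.9%. So about 30 per group instead of 16.
- Effect size: √(20.68/10.31) = 1.42 times larger. From 25% and 37.5%, that is about 35% and 53%.

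**Step 4. Does this describe the rule actually used?** No. The 80% is for a between-group ANOVA on lung MMP-9. The 0.002 is applied to mean log10 change within each arm at each time point. The power of that rule depends on the SD of change, which is not given. As an illustration only, take 25% and 37.5% as within-arm changes on the raw scale, with the implied SD of 0.34, one time point, n = 16, and an assumed baseline-to-follow-up correlation ρ. Then SD of change = 0.34 × √(2(1 − ρ)), tested by a one-sample t with 15 df at 0.002:

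| ρ | 25% decrease | 37.5% decrease |
|---|---|---|
| 0 | 10% | 34% |
| 0.5 | 28% | 74% |
| 0.7 | 56% | 96% |
| 0.8 | 80% | 99.7% |

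The result can fall on either side of 35%, and of 80%.

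**The case against.** The strongest reply is that 35% is the power of a test the trial did not report, at a design alpha that nobody stated. Both parts stand. A reader might infer that the trial had 35% power for MMP-9, or that it was more likely than not to miss the planned effects. The documents support neither. At a design level of 1% the planned ANOVA keeps 61% at 0.002, and the power of the reported intervals is unknown.

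It is also fair to say that the section already separates the analysis from the sample-size assumptions when it explains the move from ANOVA to GLMM. But it gives non-normality and unequal variance as the reasons and does not mention the cut-off, so the gap remains.

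A third reply is that a common strict threshold for all markers is conservative, and that this is a self-described pilot. That is a defensible choice, and the point here does not ask for it to be reversed. It asks that the power figure match the choice.

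What survives all three is that no power is given for the rule used, and that the 80% which is given cannot be quoted for it.

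**Conclusion.** The point holds as a mismatch between the power statement and the decision threshold. The 80% belongs to a planned ANOVA at an unstated alpha, and MMP-9 is judged at 0.002 by a different analysis. Any design level above 0.002 leaves that ANOVA short of 80% at 0.002: about 35% from a 5% design, and 24% to 61% across design levels of 10% to 1%. These figures rest on the assumed alpha, on normality with a common SD, and on 16 analysed per group.

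They do not show that the mixed-model intervals were underpowered. What the documents establish is that their power is not stated and cannot be worked out from what is given.

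**What to change.** In Data Analysis and in Sample Size Determination and Statistical Analysis:

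1. State the design alpha, and limit the 80% to the planned ANOVA at that alpha without multiplicity adjustment.
2. Add the power of that ANOVA at 0.002 (about 35% if the design level was 5%).
3. State that the 80% does not apply to the GLMM rule at 0.002, and that a null MMP-9 result must not be read as coming from an 80%-powered test.
4. State how many tests lie behind 0.002. While editing, reconcile the two pairs of effect sizes, which claim the same power from the same n.

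The cost is wording only, with a less favourable stated power.

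Moving MMP-9 to 5% is not the remedy. Enrolment ended in February 2019, and the analysis text already reports features of the observed data, so the change would be post hoc. Nor does 5% define one test. Three arms and two post-baseline days give 6 intervals for one MMP-9 measure, and 12 for active and total MMP-9 together. At 95% each, the chance of at least one false positive would be 1 − 0.95⁶ = 26% or 1 − 0.95¹² = 46% if they were independent. Any such analysis would have to be labelled post hoc and tied to one named contrast, day and MMP-9 form.
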